8 STUDY ASSESSMENTS AND PROCEDURES

The following sections describe the study procedures and data to be collected. All procedures must be performed by qualified and trained staff.

The SoA is provided in [Table 1](#).

8.1 Informed Consent

Informed consent must be obtained before any protocol-directed procedures are performed.

The requirements of the informed consent are described in [Appendix 2](#).

8.2 Demographics

Demographic information to be collected about the participant will include age/date of birth (if applicable), sex, race (and ethnicity) and medical history, including presence of any medical condition associated with high risk of severe COVID-19.

The medical conditions that constitute a high risk for COVID-19 include cancer, cerebrovascular disease, chronic kidney disease, chronic lung diseases, chronic liver disease, diabetes mellitus type 1 and type 2, heart conditions (such as heart failure, coronary artery disease, or cardiomyopathies), mental health disorders, obesity (body mass index, or $\text{BMI} \geq 30 \text{ kg/m}^2$), pregnancy and recent pregnancy, smoking (current and former), tuberculosis, disabilities including Down syndrome, HIV, neurologic conditions limited to dementia, overweight ($\text{BMI} \geq 25 \text{ kg/m}^2$ but $< 30 \text{ kg/m}^2$), sickle cell disease, solid organ or blood stem cell transplantation, substance use disorders, use of corticosteroids or other immunosuppressive medications, cystic fibrosis, asthma, physical inactivity, and immune deficiencies ([US CDC, 2023](#)).

Medication history (including medications, blood products, and vaccines) is to be collected as prior and concomitant medications.

The use of concomitant medications does not require withdrawal of the participant from the study.

Antipyretics and/or analgesic medications taken within 24 hours prior to vaccination and the reason for their use (prophylaxis versus treatment) must be documented.

Prior medications should be collected as specified in [Section 5.3](#).

Refer to [Section 5.4](#) for details on prohibited medications.

This data must be written in the source documents.

8.3 Physical Examination and Vital Signs

Physical examinations must be performed by a qualified healthcare professional in accordance with local medical practice and regulations and as listed within the site responsibility delegation log.

“Qualified healthcare practitioner” refers to any licensed healthcare professional who is permitted by institutional policy to perform physical examinations.

CONFIDENTIAL

A complete physical examination will be performed on Day 1 and may include the examination of the following: general appearance, weight, and height, abdomen; head and neck; eyes, ears, nose, throat, chest/respiratory, heart/cardiovascular, gastrointestinal/liver, musculoskeletal/extremities, dermatological/skin, thyroid, lymph nodes, and neurological. Symptom-directed physical examination may be performed at other visits if necessary.

Systolic/diastolic blood pressure, heart rate, respiratory rate, and body temperature will be measured. At vaccination visits, these assessments should be performed prior to and following study vaccination.

Vital signs should be measured in a seated position after the participant has rested comfortably for at least 5 minutes. Post vaccination, vital signs should be measured within the 30-minute observation period prior to the participant leaving the site.

This data will be written in the source document and any abnormal values or events must be documented in the eCRF AE form (if occurring after vaccination) or eCRF Medical History form (if occurring prior to vaccination). Treatment of any abnormality must be performed according to local medical practice and outside this study or by referral to an appropriate healthcare provider.

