9.1.1.1 Events Meeting the AE Definition

- Any abnormal laboratory test results (hematology, clinical chemistry, or urinalysis) or other safety assessments (e.g., electrocardiogram, radiological scans, or vital signs measurements), including those that worsen from baseline, considered clinically significant in the medical and scientific judgment of the investigator.
- Exacerbation of a chronic or intermittent pre-existing condition including either an increase in frequency and/or intensity of the condition.
- New conditions detected or diagnosed after study vaccine administration even though it may have been present before the start of the study.
- Signs, symptoms, or the clinical sequelae of a suspected drug-drug interaction.

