9.1.1.2 Events NOT Meeting the AE Definition

- Any clinically significant abnormal laboratory findings or other abnormal safety assessments which are associated with the underlying disease, unless judged by the Investigator to be more severe than expected for the participant's condition.
- Medical or surgical procedure (e.g., endoscopy, appendectomy): The condition that leads to the procedure is the AE.
- Situations in which an untoward medical occurrence did not occur (social and/or convenience admission to a hospital).
- Anticipated day-to-day fluctuations of pre-existing disease(s) or condition(s) present or detected at the start of the study that do not worsen.

CONFIDENTIAL

- Pre-existing conditions or signs and/or symptoms present in a participant prior to the first study vaccination. These events will be recorded in the medical history section of the eCRF.

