9.1.6 Assessment of Outcome of AE

The investigator will assess the outcome of all AEs recorded during the study as:

- Recovered/resolved.
- Recovering/resolving.
- Not yet recovered/not yet resolved.
- Recovered with sequelae/resolved with sequelae.
- Fatal (all fatal events are considered SAEs and should be reported accordingly).
- Unknown.

9.1.7 Time Period and Frequency for Collecting Adverse Event and Serious Adverse Event Information

Medical occurrences that begin before the study vaccination but after obtaining informed consent will be recorded in the medical history/current medical conditions section of the eCRF, not the AE section. Exacerbation of a chronic or intermittent pre-existing condition including either an increase in frequency and/or intensity of the condition after the first vaccination will be considered an AE.

For all participants:

- Any unsolicited AEs will be collected within 28 days after each vaccination.
- Any AEs that occur within 30 minutes after study vaccination are to be reported in the eCRF.
- Any AEs that are determined by the investigator (or designee) to be SAEs, AESIs (serious and nonserious), MAAEs, or AEs leading to early termination from the study or
CONFIDENTIAL

study vaccination (regardless of the causal relationship) are to be reported in the eCRF from the moment of first vaccination until completion of the participant's last study-related procedure, which may include contact for safety follow-up (until the end of the study).

All AESIs and SAEs will be recorded and reported to the Sponsor or the Sponsor's designee immediately and under no circumstance should this exceed 24 hours after the investigator becomes aware of it. The investigator will submit any updated data to the Sponsor within 24 hours of it being available.

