## 7.2 Unsolicited Adverse Events

All unsolicited AEs including SAEs, MAAEs and AESIs will be coded using MedDRA. Medical occurrences that begin before the study vaccination but after obtaining informed consent will be recorded in the medical history/current medical conditions section of the eCRF, not the AE section, all unsolicited AEs collected on the AE CRF page following the first administration will be considered TEAEs and will be included in the summaries.

Summary tables will include the number of participants (%) experiencing an event along with the number of events. Participants will be counted only once for each SOC and PT level (categorical descriptive analysis). All TEAE summaries will be presented by study group, SOC and PT.

The TEAE summaries will include:

- Overview summary of unsolicited AEs (Day 1 – Day 57)
- Summary of unsolicited AEs reported within 30 minutes after each study vaccination (derived by onset date time if event after vaccination date time) by SOC and PT. Please note that for Day 1, when 2 vaccinations are given, the 30 minutes interval is from the second vaccination.
- Summary of unsolicited AE within 28 days after each study vaccination by SOC and PT.
- Summary of related unsolicited AEs within 28 days after each study vaccination by SOC and PT
- Summary of unsolicited AE within 28 days after each study vaccination by SOC, PT and severity.
- Summary of related unsolicited AEs within 28 days after each study vaccination by SOC, PT and severity
- Summary of SAEs by SOC and PT
- Summary of related SAEs by SOC and PT
- Summary of SAEs by SOC, PT and severity
- Summary of related SAEs by SOC, PT and severity
- Summary of MAAEs by SOC and PT
- Summary of related MAAEs by SOC and PT
- Summary of AESIs by SOC and PT
- Summary of related AESIs by SOC and PT
- Summary of AEs leading to discontinuation from study by SOC and PT
- Summary of related AEs leading to discontinuation from study by SOC and PT
- Summary of (S)AEs with fatal outcome by SOC and PT

Additionally, the following summaries up to 28 days post Day 1 vaccination will be provided for Groups 2a and 2b combined (ARCT-2303), Groups 3a and 3b combined (QIV/aQIV):

- Summary of unsolicited AEs by SOC and PT
- Summary of related unsolicited AEs by SOC and PT
- Summary of SAEs by SOC and PT

For final analysis, summary of SAEs, MAAEs, AESI, AE leading to discontinuation and death will be presented cumulatively (Day 1 to EOS).

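### Protocol Section 8.3 sends every abnormal post-vaccination vital sign or examination finding to the AE form, but Section 9.1.1.1 requires clinical significance, so unsolicited-AE counts could be inflated by an amount that cannot be estimated

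*Protocol*

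**What the plan says.** - **Recording rule.** Protocol Section 8.3 covers physical examination and vital signs. It states that "any abnormal values or events must be documented in the eCRF AE form (if occurring after vaccination"), or in Medical History if they occurred before vaccination. The instruction is mandatory, does not define abnormal, and does not refer to Section 9.
- **AE definition.** Section 9.1.1.1 lists abnormal results from "other safety assessments (e.g., electrocardiogram, radiological scans, or vital signs measurements") among the events that meet the AE definition, "including those that worsen from baseline, considered clinically significant in the medical and scientific judgment of the investigator".
- **Exclusions.** Section 9.1.1.2 removes "Pre-existing conditions or signs and/or symptoms present in a participant prior to the first study vaccination" and also "Anticipated day-to-day fluctuations of pre-existing disease(s) or condition(s) present or detected at the start of the study that do not worsen".
- **Route to the tables.** SAP Section 7.2 states that "all unsolicited AEs collected on the AE CRF page following the first administration will be considered TEAEs and will be included in the summaries". The same section plans a table of unsolicited AEs within 30 minutes of each vaccination.
- **Collection window.** Section 9.1.7: "Any unsolicited AEs will be collected within 28 days after each vaccination".
- **Subgroups.** SAP Section 3.9 plans unsolicited-AE summaries by country at the second final analysis.

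**The concern.** Two sections of one protocol give different rules for the same reading. A blood pressure that is abnormal, newly seen after injection and judged not clinically significant must go on the AE form under 8.3. Under 9.1.1.1 it is not an AE.

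Unsolicited AEs within 28 days are part of the secondary safety objective. Vital signs are taken in all of the roughly 1680 participants before and after each vaccination and again at Day 57, so there are many chances for the conflict to arise. Section 8.3 places the post-dose measurement inside the 30-minute observation period, so such an entry also falls within the immediate-event table.

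Sites that follow 8.3 would report more AEs than sites that follow 9.1.1.1. If the choice of rule clusters by country, recording practice could look like a country difference in the subgroup summaries.

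**Working it through.** The plan states no figure on this point, so there is nothing to reproduce. The check has two parts.

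**1. The rules side by side, for a finding after the first vaccination**

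| Finding | Section 8.3 | Sections 9.1.1.1 and 9.1.1.2 |
|---|---|---|
| New, clinically significant | AE form | AE |
| New, not clinically significant | AE form | Not an AE |
| Abnormal before vaccination, not worse after | Disputable: Medical History for the earlier reading, AE form for the later one if read literally | Not an AE |

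The second row is a plain contradiction. The third is an ambiguity. A Day 29 pre-dose reading adds another, because it is after one vaccination and before the next.

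Nothing downstream resolves the conflict. SAP 7.2 takes AE-page entries as they stand. The SAP lists abbreviations for clinically significant and not clinically significant, but its vital-signs section (7.3) does not use them.

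**2. How large the effect could be (illustration only)**

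Inputs:
- Five measures per set: systolic and diastolic pressure, heart rate, respiratory rate and temperature (SAP 7.3).
- Two sets in the first 28-day window: Day 1 post-dose and Day 29 pre-dose (Protocol Table 1, footnote e). This gives k = 10 readings.
- k = 8 if temperature is left out, because fever is a solicited event (Section 9.1.9).
- Background 14.0%: unsolicited AEs within 28 days of the first ARCT-154 dose in study ARCT-154-01 (Protocol Section 2.1.2).
- q, the chance that one reading is newly abnormal. **This is assumed, from 0.05% to 5%; no document gives it.**

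Formulas, with readings treated as independent of each other and of other AEs:

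x = 1 − (1 − q)^k, and inflated rate = 1 − (1 − 0.140)(1 − x).

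For example, with q = 1% and k = 10: x = 1 − 0.99^10 = 9.6%, and the rate is 1 − 0.86 × 0.904 = 22.2%.

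| q per reading | x, k = 10 | Rate, k = 10 | x, k = 8 | Rate, k = 8 |
|---|---|---|---|---|
| 0.05% | 0.5% | 14.4% | 0.4% | 14.3% |
| 0.1% | 1.0% | 14.9% | 0.8% | 14.7% |
| 0.5% | 4.9% | 18.2% | 3.9% | 17.4% |
| 1% | 9.6% | 22.2% | 7.7% | 20.6% |
| 2% | 18.3% | 29.7% | 14.9% | 26.8% |
| 5% | 40.1% | 48.5% | 33.7% | 42.9% |

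Vital-sign entries alone would equal the 14.0% background at q = 1 − 0.86^(1/10) = 1.5% (k = 10), or 1 − 0.86^(1/8) = 1.9% (k = 8).

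For the 30-minute table a single post-dose set counts. With q of 1%, 2% or 5%, five measures give 4.9%, 9.6% or 22.6% of participants, and four measures give 3.9%, 7.8% or 18.5%.

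Positive correlation between systolic and diastolic pressure, or between repeat readings in one person, would lower all of these. The range runs from negligible to dominant, and the documents cannot narrow it.

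**The case against.** **Section 9 governs.** Section 8.11 refers the reader to Section 9 for safety definitions. The opening of Section 9 makes investigators responsible for events that meet the AE definition, and 9.1.3 prefers a diagnosis to individual signs. On this view 8.3 says only where an abnormality is filed. This shows the likely intent, and many sites would act on it. It does not cancel a mandatory sentence that carries no cross-reference and no qualifier.

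**The effect may be trivial.** This stands. A reader might infer that out-of-range readings would swamp the endpoint, and the documents do not support that. Section 8.3 speaks of abnormal values, not of a programmed range flag, and no limits are given. It would also be wrong to count all four sets through Day 57 (20 readings, giving 18%, 33% or 64% at q of 1%, 2% or 5%) against 14.0%. Those sets span two vaccination windows and the comparator covers one.

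**Baseline abnormality is handled.** This largely stands. A participant with stable hypertension and similar readings before and after injection looks like a clear case, but Medical History takes abnormalities that occur before vaccination. The firm contradiction concerns new findings judged not clinically significant.

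**No bias between arms.** This stands. Observers are blinded and allocation is 1:1:1, so site practice should be unrelated to arm, and the absence of site stratification does not change that. Tables by preferred term would also let a reader see blood-pressure entries rather than lose them in a total.

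**Conclusion.** The contradiction is real and can be read directly from the text: 8.3 requires an AE entry that 9.1.1.1 would reject, and SAP 7.2 counts the entry. The likely harm is inflation of the unsolicited-AE and 30-minute percentages, dilution of relative contrasts between arms, and possible noise in the country subgroups.

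The size cannot be estimated from the documents. The range of 14.4% to 48.5% around a 14.0% background rests on an assumed q, on independence, and on every site following 8.3 literally. It marks out what is not known and is not a forecast.

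The consequence is bounded. The endpoint is secondary and descriptive (Protocol Section 10.1 plans no formal safety test), no difference between blinded arms is expected, and the primary hypotheses, alpha and power are unaffected. No SAP analysis is wrong in itself; the fault lies in the data-collection instruction that feeds it. It is worth correcting because the remedy costs so little.

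**What to change.** Reconcile Section 8.3 with 9.1.1.1 and 9.1.1.2. State in 8.3, and in the eCRF completion guideline, that a post-vaccination abnormal finding goes on the AE form only if it meets the AE definition in Section 9.1.1. State also how a Day 29 pre-dose abnormality is to be classed. Keep all other readings in the vital-signs data.

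The cost is one or two sentences in the protocol and the guideline, with no extra data or participants. No vital-sign information is lost, because SAP 7.3 already summarises scheduled vital signs and their change from baseline, and lists unscheduled ones.

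If data have already been entered under the present wording, a count by country of AE-page entries that consist only of a vital-sign reading would show whether the issue mattered in practice.

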8.4 Pregnancy Testing

A urine pregnancy test will be conducted for women of childbearing potential prior to study vaccination (see [Section 9.1.13](#)). Blood pregnancy testing may be performed at the investigator's discretion or in accordance with institutional policy or local requirements. A positive pregnancy test will prevent study vaccination.

8.5 Rapid COVID-19 Antigen Test

A SARS-CoV-2 Rapid Antigen Test or equivalent will be performed on site prior to each study vaccination to confirm that a participant is eligible for vaccination. A positive test will prevent study vaccination.

8.6 ECG/Cardiac Enzymes Test

A baseline 12-lead ECG will be performed at recruitment on all study participants to identify potential asymptomatic myocarditis and pericarditis cases.

In case of suspected myocarditis or pericarditis cases during the study period, detailed evaluation, including ECG, cardiac enzyme testing, and other relevant data should be evaluated.

Additional ECG evaluation at unscheduled visits is at the investigator's discretion.

Blood samples for cardiac enzymes will be collected on Day 1 prior to vaccination (baseline) in all participants. The testing of baseline and post-vaccination samples for cardiac enzymes may be performed at the investigator's or Sponsor's discretion.

8.7 Inclusion and Exclusion Criteria

Only participants who have a signed ICF and satisfy all of the inclusion ([Section 5.1](#)) and exclusion ([Section 5.2](#)) criteria are eligible for randomization and to enter the study.

CONFIDENTIAL

May not be used, divulged, published or otherwise disclosed without written consent of Arcturus Therapeutics, Inc.

If the participant is ineligible for randomization, the investigator should record the primary reason for failure on the participant screening and enrollment log ([Section 5.6](#)).

8.8 Randomization

An interactive response technology (IRT) system will be used. Participants will be randomized in a 1:1:1 ratio to each study arm. Randomization will be stratified by COVID-19 vaccination history (such as a total number of COVID-19 vaccine doses received and the composition of the last booster dose (mRNA original strain or mRNA bivalent)). The randomization specification and schedule will be approved by the Sponsor's study statistician, or designee.

8.9 Vaccination

All participants will be monitored for 30 minutes after study injection for any immediate adverse reactions.

The instructions regarding study vaccine preparation and administration are provided in [Section 6 Study Treatment](#), the pharmacy manual and package insert document for control vaccine.

8.10 Immunogenicity Assessments

Humoral immune responses against SARS-CoV-2 will be assessed in Groups 1a and 1b, Groups 2a and 2b, and a set of samples from study ARCT-154-J01 using the following assays:

- Virus neutralizing assay (VNA, neutralizing antibodies against SARS-CoV-2) with Omicron XBB.1.5 subvariant;
- VNA (neutralizing antibodies against SARS-CoV-2 using various epidemiologically relevant SARS-CoV-2 variants)

Results from VNAs will be analyzed as:

- Geometric mean titer (GMT) on Days 1, 29 and 181;
- Geometric mean-fold rise (GMFR) as increases of the post-vaccination titer over the pre-vaccination titer;
- Seroconversion rate (SCR) on Day 29 as the percentage of participants in each arm with either:
 - A pre-vaccination titer below the lower limit of quantitation (LLOQ) and a postvaccination titer $\geq 4 \times$ LLOQ; or
 - A pre-vaccination titer \geq LLOQ and a ≥ 4 -fold increase in post-vaccination titer.
- Proportion of participants with antibody titer \geq LLOQ.

Humoral immune responses against QIV will be assessed in Groups 1a and 1b, and Groups 3a and 3b using the following assays:

- Hemagglutination Inhibition (HI) assay against influenza vaccine strains. In case of lack of agglutination for a specific strain using HI assay, immunogenicity for that strain will be assessed as measured by microneutralization (MN) assay;
- MN titers against influenza vaccine strains.

CONFIDENTIAL

The results of HI and MN will be analyzed as:

- Geometric mean titer (GMT) on Days 1 and 29;
- Geometric mean-fold ratio (GMFR) as increases of the post-vaccination titer over the pre-vaccination titer;
- SCR on Day 29 as the percentage of participants in a group with either:
 - A pre-vaccination titer below the LLOQ for the respective assay and a post-vaccination titer $\geq 4 \times \text{LLOQ}$; or
 - A pre-vaccination titer $\geq \text{LLOQ}$ and a ≥ 4 -fold increase in post-vaccination titer.
- Proportion of participants with HI titer $\geq 1:10, 1:20, 1:40, 1:80, 1:160$ and $1:320$ on Days 1 and 29;
- Proportion of participants with MN titer $\geq \geq 1:10, 1:20, 1:40, 1:80, 1:160$ and $1:320$ on Days 1 and 29.

Planned time points for all immunogenicity assessments are provided in the SoA ([Table 1](#)).

8.10.1 Blood Volumes and Serological Testing

All analyses will be performed at a laboratory designated by the Sponsor or the Sponsor's designee using standardized and validated procedures.

The maximum volume of blood taken at any single visit is 30 mL, and the maximum total volume of blood collected during the study period in each study participant is approximately 90 mL. All samples listed in [Table 6](#) will be drawn in all participants.

On Days 1 and 29, all samples from prespecified study arms will be tested using VNA with Omicron XBB.1.5 subvariant, and hemagglutination inhibition assay. A random subset of samples from Groups 2a and 2b will be tested using VNA to assess antibody persistence at Day 181 and to evaluate cross-neutralization of epidemiologically relevant variants of SARS-CoV-2 on Days 1 and 29. The random selection process of samples will be described in the Statistical Analysis Plan.

In case of lack of agglutination for a specific strain using the HI assay, a microneutralization assay will be used for the respective strain.

The testing plan is provided in [Table 6](#).

CONFIDENTIAL

Table 6 Testing Plan for ARCT-2303-01

| Assay | Study Arms | Day 1 N | Day 29 N | Day 181 N |
|---|--|---|--|---|
| VNA (Omicron XBB.1.5) | Group 1a Group 1b Group 2a Group 2b ARCT-154-J01 study | 400 (all) 160 (all) 400 (all) 160 (all) ~385 | 400 (all) 160 (all) 400 (all) 160 (all) ~385 | — — 100 (subset) 100 (subset) — |
| Hemagglutination Inhibition assay (H1N1, H3N2, 2B) | Group 1a Group 1b Group 3a Group 3b | 400 (all) 160 (all) 400 (all) 160 (all) | 400 (all) 160 (all) 400 (all) 160 (all) | — — — — |
| Microneutralization assay (H1N1, H3N2, 2B) | Group 1a Group 1b Group 3a Group 3b | In case of lack of agglutination for a specific strain using HI assay | | — |
| VNA (various lineages, including any prevalent variant) | Group 2a | 50 (subset) | 50 (subset) | — |
| Total maximum volume/ each participant | | 30 mL | 30 mL | 30 mL |

Abbreviations: N: number of participants per timepoint; VNA, virus neutralizing assay; Safety testing may be performed in case of suspected myocarditis or pericarditis or other safety concerns

